### **4.5.2.3 Same as primary and secondary endpoints**

Primary and secondary endpoints up to Week 24 will be summarized each visit. These endpoints after Week 24 up to Week 52 will be summarized each visit by dose regimen group and overall. Imputation will not be used.

## **4.6 MULTIPLICITY ISSUES**

No hypothesis testing will be performed within this study.

## **4.7 SAFETY ANALYSES**

### **4.7.1 Extent of exposure**

The extent of IMP exposure will be assessed by the duration of IMP exposure and compliance and summarized within the Safety population until Week 24 and the Safety for extension term population after Week 24.

If needed, extent of exposure to investigational medicinal product will be summarized for participants experiencing disruption due to COVID-19.

The participants who received COVID-19 vaccines are summarized.

### **Duration of IMP exposure**

Duration of IMP exposure is defined as last IMP date – first IMP date

- + 14 days at the time of last IMP for the q2w group and
- + 28 days at the time of last IMP for the q4w regimen,

regardless of unplanned intermittent discontinuations. If the date of the last dose of IMP is missing, the duration of IMP will be left as missing.

Duration of IMP exposure will be summarized quantitatively and categorically: 1 to 2 weeks, 3 to 4 weeks, 5 to 8 weeks, 9 to 12 weeks, 13 to 18 weeks, 19 to 24 weeks, 25 to 30 weeks, 31 to 36 weeks, 37 to 42 weeks, 43 to 48 weeks, 48 to 52 weeks, and >52 weeks. The duration of treatment exposure in weeks will be the duration (in days)/7, rounded to the nearest integer.

Duration of study will be summarized separately and analyzed descriptively as a quantitative variable (number, mean, SD, median, minimum, and maximum). The duration of study is defined as date of study completion (or discontinuation) – date of first dose of IMP + 1.

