This is a Phase 4, open-label, single-arm, multicenter, efficacy and safety study of dupilumab monotherapy in participants with CRSwNP that is not adequately controlled with existing therapies.

This study will investigate the efficacy and safety of dupilumab 300 mg every 2 weeks (q2w) at Week 24, without concomitant administration of INCS.

In addition, in line with Japan label, the study is designed to assess the long-term (52 weeks) efficacy and safety of an initial treatment regimen of dupilumab 300 mg q2w for 24 weeks without INCS, followed by a less frequent dosing regimen (300 mg every 4 weeks [q4w]) up to Week 48 for those participants who demonstrate stable disease* at Week 24. Other participants will receive the q2w regimen up to Week 50.

**Stable disease definition: nasal polyp score (NPS) improvement from baseline to both Weeks 16 and 24 is ≥ 2 points.*

During the study, participants who report deterioration requiring medical or surgical intervention may go to the study site for clinical evaluation. An unscheduled visit may be used for this purpose, and if necessary, the Investigator may consider one of the treatment alternatives described in [Section 6.8.1](#).

Brief summary:

This is a Phase 4, open-label, single-arm, multicenter study to evaluate the efficacy and safety of dupilumab monotherapy in participants aged 18 or older with CRSwNP that is not adequately controlled with existing therapies.

Number of participants:

Approximately 25 participants will be enrolled.

Intervention groups and duration:

Study intervention(s)

- Dupilumab 300 mg q2w
- Dupilumab 300 mg q4w

For participants who have stable disease, the dosing interval can be changed from q2w to q4w at the discretion of the Investigator at Week 24. Participants who change from q2w to q4w will not be permitted to return to the q2w regimen during this study and will receive the q4w regimen until Week 48. Other participants will receive the q2w regimen up to Week 50. The participants will be followed up to Week 52.

Duration of study period (per participant):

- Screening Period (2 to 4 weeks): between Screening Visit (Visit 1) and the first dose of investigational medicinal product (IMP) (Visit 2)
- Intervention Period (up to 52 weeks±3 days)

Investigational medicinal product(s):

- Dupilumab 300 mg

Formulation:

- Dupilumab 300 mg: a 150 mg/mL dupilumab solution in a prefilled syringe to deliver 300 mg in a 2-mL injection

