- a Past medical history, including allergic comorbidities (asthma, aspirin sensitivity, allergic rhinitis, etc.). Surgeries for NP, including number, type and dates of sinonasal surgeries, and polypectomies, in the past will be recorded. Systemic corticosteroid use (number of courses, doses, route of administration, and duration) in the past 2 years before V1 and/or contraindication/intolerance to SCS, as well as long-term antibiotics use (>2 weeks) in the previous year, will be entered in the e-CRF. NERD will be assessed through a specific questionnaire (Appendix 11 [Section 10.11]).
- b Call IVRS/IWRS to register visit and obtain next IMP kit numbers assignment or report potential definitive IMP stop.
- c Investigational medicinal product will be administered q2w (after Week 24, some participants can be administered q4w). Between visits, at site or home administration is allowed after the second dose. Investigational medicinal product will be administered after the completion of all scheduled clinical assessments at the visit or at home. The planned last dose is at Week 48 or 50. For participants who have stable disease at Week 24, the dosing interval can be changed from q2w to q4w at the discretion of the Investigator; the reason for the change in dosing regimen should be recorded in the e-CRF. Other participants will receive the q2w regimen until Week 50. Stable disease is defined as NPS improvement from baseline to both Weeks 16 and 24 of ≥ 2 points.
- d Nasal endoscopy: endoscopy (including use of decongestants before the procedure) will be performed after all other efficacy assessments have been completed for each visit. Standard video sequences will be downloaded by the Investigator to the central reader's secured internet site. For eligibility, central reading of V1 will be used. At V2, the Investigator will review the V1 results from the central reader to confirm entry criteria and reconfirm eligibility based on a review of the inclusion/exclusion criteria and the V2 endoscopy local reading. To confirm eligibility at V2, only the V1 central reading will be made available to the site. In addition, at V2, the Investigator will perform the NE to confirm eligibility score and enter the result in the e-CRF. Thus, the participant will be considered eligible based on a V1 central reading followed by a V2 local reading NPS score of 5 or more and at least 2 on each side.
- e Computerized tomography scan to be done during the Screening Period.

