##### *Treatment Duration when IMP end date is missing*

For the calculation of the treatment duration, the date of the last dose of IMP is equal to the date of last administration reported on the end-of-treatment case report form page. If this date is missing, the exposure duration should be left as missing.

The last dose intake should be clearly identified in the case report form and should not be approximated by the last returned package date.

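### SAP 4.7.1 splits the exposure summary at Week 24, but its only formula covers the whole study, so a completer shows 52 weeks in both tables

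*SAP*

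**What the plan says.** SAP 4.7.1 (Extent of exposure) says that duration of exposure and compliance will be "summarized within the Safety population until Week 24 and the Safety for extension term population after Week 24". This is the same split that SAP 4.1 and 4.7.2 apply to the other safety data, with the extension shown by dose regimen group and overall.

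Under Duration of IMP exposure there is one definition: "Duration of IMP exposure is defined as last IMP date – first IMP date". To this is added "14 days at the time of last IMP for the q2w group and" "28 days at the time of last IMP for the q4w regimen". Nothing cuts the formula off at Week 24 or restarts it for the extension.

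SAP 5.4.4 says which date is meant: "the date of the last dose of IMP is equal to the date of last administration reported on the end-of-treatment case report form page". That is the last dose of the study, not the last dose of a period.

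Durations are then converted to weeks, rounded to the nearest integer and put into one list of categories that runs to more than 52 weeks. Two neighbouring entries are "43 to 48 weeks, 48 to 52 weeks".

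**The concern.** SAF contains everyone dosed before Week 24, including those who go on to Week 52. SAFE contains those dosed after Week 24, all but late starters of whom also have 24 weeks of earlier dosing. A whole-study formula applied to both populations therefore gives the same participant the same number twice, and neither number is the exposure during the period named for the table.

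Exposure tables give the context for reading adverse event tables. Here the adverse events are cut at Week 24 and the exposure is not. The regimen split adds a second mismatch: exposure shown for the q4w group in the extension would include the q2w dosing that those participants received before Week 24.

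The category list has a smaller fault of its own. Because durations are rounded to whole weeks, a value of 48 satisfies two entries and the SAP has no rule for choosing between them.

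**Working it through.** **Inputs.** First dose at Week 0. Last dose: "The planned last dose is at Week 48 or 50" (Protocol, Schedule of Activities footnote c), that is Week 48 for q4w and Week 50 for q2w. Add-on of 14 or 28 days (SAP 4.7.1). Planned treatment length: "Intervention Period (up to 52 weeks±3 days" (Protocol 1.1).

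**Step 1. The formula as written, for a completer.** Duration = (last week − first week) × 7 + add-on.

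- q2w: 50 × 7 + 14 = 364 days; 364 / 7 = 52 weeks.
- q4w: 48 × 7 + 28 = 364 days; 364 / 7 = 52 weeks.

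This reproduces the planned 52 weeks, and a shift of 3 days either way still rounds to 52. The formula is therefore sound for the whole study. The difficulty is that nothing limits it to a period, so 52 goes into both tables.

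**Step 2. Period values, with the Week 24 dose in the extension.**

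- Up to Week 24 (doses Week 0 to 22): 22 × 7 + 14 = 168 days = 24 weeks.
- Extension, q2w (Week 24 to 50): 26 × 7 + 14 = 196 days = 28 weeks.
- Extension, q4w (Week 24 to 48): 24 × 7 + 28 = 196 days = 28 weeks.

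The two parts add up: 24 + 28 = 52. On this basis 52 weeks overstates a completer's exposure by 52 / 24 − 1 = 117% in the SAF table and by 52 / 28 − 1 = 86% in the SAFE table.

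**Step 3. The other assignment.** Put the Week 24 dose in the first period and do not cap the add-on.

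- First period: (24 × 7 + 14) / 7 = 26 weeks, or (24 × 7 + 28) / 7 = 28 weeks with the q4w add-on.
- Second period, q2w (Week 26 to 50): (24 × 7 + 14) / 7 = 26 weeks.
- Second period, q4w (Week 28 to 48): (20 × 7 + 28) / 7 = 24 weeks.

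So even a programmer who infers a split could reach 24, 26 or 28 weeks for either period.

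**Step 4. Non-completers.** A participant whose last dose is at Week 10 gets (70 + 14) / 7 = 12 weeks, which is right for the SAF table. For a participant who started on schedule and stopped soon after Week 24, the SAFE value as written is still about 26 weeks (only the Week 24 dose, q2w: (168 + 14) / 7) to 32 weeks (only the Week 28 dose, q4w: (196 + 28) / 7), because the first 24 weeks are included.

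**Step 5. Categories.** Checking each integer from 1 upwards against the list, only 48 falls in two categories. It covers 333 days (47.57 weeks) to 339 days (48.43 weeks). Examples are a q2w participant last dosed at Week 46, (322 + 14) / 7 = 48, and a q4w participant last dosed at Week 44, (308 + 28) / 7 = 48.

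**The case against.** The best defence is that the opening sentence of SAP 4.7.1 already sets the period and the formula below it is generic, to be applied within that period. The wording does suggest that a period-specific summary was intended. But no period-specific first or last dose is defined, SAP 5.4.4 ties the last dose to the end-of-treatment page, and the one category list runs past 52 weeks. Step 3 shows that the intention alone does not fix the number.

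Other parts of the defence stand. A reader might infer that adverse event frequency per unit of time will look about half its true size. The documents do not support that: adverse events are reported as the number and percentage of participants with at least one event, the safety population is the denominator, and no exposure-adjusted rate is planned. A reader might also infer that exposure is counted twice, but the SAP never adds the two tables together.

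The category overlap is very probably a slip, since every other boundary in the list is exclusive. Double counting is not inevitable either, because a categorical variable normally takes one value per participant. What remains is that the SAP does not say which value, for what would be few of about 25 participants.

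**Conclusion.** The exposure rule is wrong as written for the tables it is meant to fill. A completer on either regimen shows 52 weeks in both, against 24 and 28 weeks when the Week 24 dose belongs to the extension, or 24 to 28 weeks per period under other assignments. The 117% and 86% overstatements hold for completers under the first assignment only. Participants who stop before Week 24 have a correct value in the SAF table. In the extension table, a q4w completer's 52 weeks include 24 weeks of q2w dosing.

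The consequence is limited to descriptive safety tables: exposure that does not match the period of the adverse events beside it, and one week value without a unique category. No adverse event percentage, efficacy estimate or conclusion changes. The point is minor, but worth correcting because the text gives a definite number for the wrong period.

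**What to change.** Define exposure within each period, using the Week 24 date that the q4w compliance formula in SAP 4.7.1 already uses as its split. A date works better than the Week 24 dose, because a participant may miss that dose and still be in SAFE.

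- **Up to Week 24 (SAF):** last dose before the Week 24 date − first dose + 14 days, capped at the Week 24 date.
- **Extension (SAFE):** last dose − first dose on or after the Week 24 date, + 14 days (q2w) or + 28 days (q4w).
- **Whole study:** keep the present formula as a separate summary.
- **Compliance:** apply the same split. Its denominator also runs from first to last injection of the study, although 4.7.1 reports it by period; the q4w formula uses the Week 24 date but adds both parts into one count.
- **Categories:** change 48 to 52 weeks to 49 to 52 weeks, so that week 48 falls in one category only.

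The SAP should also say what the Week 24 date is when that visit is missed; the Day 169 target in SAP Table 10 is one candidate. If a single whole-study exposure table is what the sponsor wants, the split in the opening sentence of 4.7.1 should be removed instead. Either way the cost is a few lines of SAP text and minor programming, with no new data.

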### **Treatment compliance**

A given administration will be considered noncompliant if the participant did not take the planned number of doses as required by the protocol.

Percentage of treatment compliance for a participant will be defined as the number of injections (a partial injection will be counted as 1 injection) a participant took divided by the total number of planned injections from the first to the last injection of IMP \*100. Number of planned injections is calculated as:

- For q2w participants,  
 $1 + (\text{last dose date} - \text{first dose date} + 1)/14$ , rounded to the nearest integer
- For q4w participants,  
 $1 + [(\text{Week 24 date} - 1) - \text{first dose date} + 1]/14 +$   
 $(\text{last dose date} - \text{Week 24 date} + 1)/28$ , rounded to the nearest integer

Treatment compliance will be summarized descriptively as quantitative variables (number, mean, SD, median, minimum, and maximum). The percentage of participants whose compliance is <60, ≥60 and <80, ≥80% and ≤100%, or >100% will be summarized.

### **4.7.2 Adverse events**

#### **General common rules for adverse events**

All safety analyses up to Week 24 will be analyzed for the SAF. Safety data collected during the extension term after Week 24 up to Week 52 will be reported for the SAFE. Safety analyses for the extension term will be presented by dose regimen group and overall.

All adverse events (AEs) will be coded to a lower-level term (LLT), preferred term (PT), high-level term (HLT), high-level group term (HLGT), and associated primary system organ class (SOC) using the latest MedDRA version currently in effect at the time of DBL.

AEs will be categorized as:

- Pre-treatment AEs: AEs that developed, worsened or became serious during the pre-treatment period.
- Treatment-emergent adverse events (TEAE)s: AEs that developed, worsened or became serious during the treatment-emergent period
- Post-treatment AEs: AEs that developed, worsened or became serious after the treatment-emergent period.

Similarly, deaths will be categorized in the pre-treatment and treatment-emergent periods.

The primary focus of AE reporting will be on TEAEs. Pre-treatment AEs will be described separately.

An AE with incomplete or missing date/time of onset will be classified as a TEAE unless there is definitive information to determine it is a pre-treatment AE.

If the assessment of the relationship to IMP is missing for an AE, this AE will be assumed as related to IMP. If severity is missing for 1 of the treatment-emergent occurrences of an AE, the severity will be imputed as the maximal severity of the other occurrences. If the severity is missing for all the occurrences, severity will be left as missing.

Multiple occurrences of the same event in the same participant will be counted only once in the tables within a treatment phase.

The AE tables will be sorted as indicated in [Table 7](#).

**Table 7 - Sorting of AE tables**

AE presentation	Sorting rules
SOC, HLGT, HLT and PT	By the internationally agreed SOC order and by alphabetic order of HLGTs, HLTs and PTs.
SOC and PT	By the internationally agreed SOC order and decreasing frequency of PTs a .
SMQ/CMQ and PT	By decreasing frequency of SMQs/CMQs and PTs
SOC	By the internationally agreed SOC order
PT	By decreasing frequency of PTs

a The table of all TEAEs presented by SOC and PT will define the presentation order for all other tables (eg, treatment-emergent SAE) presented by SOC and PT, unless otherwise specified.

### **Analysis of all adverse events**

The overview of TEAE with the details below will be generated:

- Any TEAE
- Any severe TEAE
- Any TEAE related to IMP

- Any treatment emergent SAE
- Any treatment emergent SAE related to IMP
- TEAE leading to death
- Any TEAE leading to permanent treatment discontinuation
- Any treatment emergent AE of special interest (AESI)

The AE summaries in [Table 8](#) will be generated with number (%) of participants experiencing at least one event.

**Table 8 - Analyses of adverse events**

Type of AE	MedDRA levels
Overview	
TEAE	Primary SOC, HGLT, HLT and PT Primary SOC and PT Primary SOC PT
TEAE related to IMP as per Investigator's judgment	Primary SOC, and PT
Treatment emergent SAE	Primary SOC, HGLT, HLT and PT
TEAE leading to permanent discontinuation	Primary SOC, HGLT, HLT and PT
TEAE leading to death (death as an outcome of the AE as reported by the Investigator in the AE page)	Primary SOC, HGLT, HLT and PT
TEAE by maximal intensity	Primary SOC, HGLT, HLT and PT
Pretreatment AE	Primary SOC, HGLT, HLT and PT
Post-treatment AE	Primary SOC, HGLT, HLT and PT
TEAE(s) related to COVID-19	Primary SOC, HGLT, HLT and PT
TEAE(s) occurred within 2 weeks of a COVID-19 vaccine	Primary SOC, HGLT, HLT and PT

a Will include the following AE categories: any AEs, AEs by severity, any related AEs, any serious AEs, any related serious AEs, any AEs leading to death, any AEs leading to permanent IMP discontinuation

### **Analysis of adverse events of special interest (AESIs)**

Adverse events of special interest (AESIs) will be selected for analyses as indicated in [Table 9](#). Number (%) of participants experiencing at least one event will be provided for each event of interest, sorted by decreasing incidence of PTs within each SMQ in the 300 q2w . Tables will be sorted as indicated in [Table 7](#).

**Table 9 - Selections for AESIs and other AEs of interest**

AESIs [and other AEs of interest]	Selection
AESI	
Anaphylactic reactions	Anaphylactic reaction algorithmic approach (Introductory Guide for Standardised MedDRA Queries (SMQs)): includes anaphylactic reaction narrow SMQ (2000021) terms and programmatic identification of cases based on occurrence of at least two preferred terms meeting the algorithm criteria occurring within 24 hours of each other. The latter cases identified using the algorithm will undergo blinded medical review taking into account the timing of events relative to each other and to IMP administration for final determination of an anaphylactic reaction or not.
Systemic hypersensitivity reactions	SMQ [20000214] hypersensitivity narrow search and [AE corrective treatment/therapy='Y' or Action taken with IMP='Drug withdrawn' or Action taken with IMP='Drug interrupted'] followed by blinded medical review (documented process) for selection of relevant systemic hypersensitivity events
Helminthic infections	CMQ10544 based on HLT as "Helminthic disorder"
Any severe type of conjunctivitis	CMQ10498 based on PTs (See Section 5.6)a and "Severe" ticked in Adverse Events eCRF page
Any severe type of blepharitis.	CMQ10497 based on HLT as "Lid, lash and lacrimal infections, irritations and inflammations" and "Severe" ticked in Adverse Events eCRF page
Keratitis	CMQ10642 based on the following PTs [keratitis, allergic keratitis, ulcerative keratitis, atopic keratoconjunctivitis, herpes ophthalmic, ophthalmic herpes simplex, corneal infection]a
Clinically symptomatic eosinophilia (or eosinophilia associated with clinical symptoms)b	CMQ10641 based on HLT = Eosinophilic disorders or PT=Eosinophil count increased
Significant ALT elevation	ALT >5 × the ULN in participants with baseline ALT ≤2 × ULN for age; OR ALT >8 × ULN for age if baseline ALT >2 × ULN for age
Pregnancy of a female subject entered in a study as well as pregnancy occurring in a female partner of a male subject entered in a study with IMP/NIMP	"Pregnancy" or "Partner Pregnancy" checked on thePregnancy eCRF page as reported by the investigator
Symptomatic overdose (serious or nonserious) with IMP/NIMP.	Symptomatic Overdose is answered Yes, with Overdose of IMP answered Yes on AE eCRF.
Other selected AE Grouping	
Serious injection site reactions or severe injection site reactions that last longer than 24 hours	HLT = 'Injection site reaction' and either with serious status, or with severe status and (AE end date/time - AE start date/time) ≥ 24 hours or ongoing
Severe or serious infection	Primary SOC = 'Infections and infestations' and with severe or serious status
Parasitic infection	The Infection Type 'Parasitic' was checked on eCRF page "Infection Defined as AESI Complementary Form"
Opportunistic infection	The Infection Type 'Opportunistic' was checked Yes on eCRF page "Infection Defined as AESI Complementary Form"

AESIs [and other AEs of interest]	Selection
Drug-related hepatic disorder	SMQ [20000006] Drug-related hepatic disorders- narrow
Injection site reaction	HLT = 'Injection site reaction'
Suicidal behavior	CMQ10639 based on the following PTs [Completed suicide, Suicidal ideation, Depression suicidal, Suicidal behavior, Suicide attempt] a
Conjunctivitis (narrow)	CMQ10644 based on the following PTs [Conjunctivitis, Conjunctivitis allergic, Conjunctivitis bacterial, Conjunctivitis viral, Atopic keratoconjunctivitis] a
Conjunctivitis (broad)	CMQ10645 based on the following PTs [Conjunctivitis, Conjunctivitis allergic, Conjunctivitis bacterial, Conjunctivitis viral, Atopic keratoconjunctivitis, Blepharitis, Dry eye, Eye irritation, Eye pruritus, Lacrimation increased, Eye discharge, Foreign body sensation in eyes, Photophobia, Xerophthalmia, Ocular hyperaemia, Conjunctival hyperaemia] a
Conjunctivitis (FDA)	CMQ10643 based on the following PTs [Conjunctivitis, Conjunctivitis allergic, Conjunctivitis bacterial, Conjunctivitis viral, Eye irritation, Eye inflammation, Giant papillary conjunctivitis] a

a The list of terms may be adjusted according to MedDRA version changes

b All cases of Eosinophilia will be included in the analysis, where cases associated with clinical symptoms will be further described in the CSR

